7.3. Serious Adverse Events (SAEs)

An SAE is defined as any untoward medical occurrence that at any dose (ICH E2A and E6 R1):

- Results in death.
- Is life-threatening.
This means that the subject is at risk of death at the time of the event; it does not mean that the event hypothetically might have caused death if it were more severe.
- Requires inpatient hospitalization or prolongation of existing hospitalization.
- Results in persistent or significant disability or incapacity.
- Is a congenital anomaly or birth defect.

Other important medical events that may not be immediately life-threatening or result in death or hospitalization, based upon appropriate medical judgment, are considered SAEs if they are thought to jeopardize the subject and/or require medical or surgical intervention to prevent one of the outcomes defining a SAE.

Since SAEs are critically important for the identification of significant safety problems, it is important to take into account both the Investigator's and the sponsor's assessment. If either the sponsor or investigator believes that the event is serious, the event must be considered serious and evaluated by the Sponsor for expedited reporting.

All SAEs must be reported to the sponsor or sponsor designee immediately after the Investigator becomes aware of the event, along with a determination as to whether it is associated with the IP or any other study procedure.

Disease progression should not be recorded as an AE or SAE term; instead, signs and symptoms of clinical sequelae resulting from disease progression will be reported if they fulfill the SAE definition.

7.4. Serious Adverse Event Reporting

All SAEs, irrespective of relationship to IP, must be reported within 24 hours of the Investigator knowledge of the event to the Sponsor or CRO. In particular, if the SAE is fatal or life-threatening, notification to the Sponsor must be made immediately, irrespective of the extent of available AE information. This timeframe also applies to follow-up information on previously forwarded SAE reports as well as to the initial and follow-up reporting of exposure during pregnancy and exposure via breast feeding cases.

Relevant medical records should be provided to the Sponsor or CRO as soon as they become available; autopsy reports should be provided for deaths if available. Should an Investigator be made aware of an SAE occurring any time after the reporting period, it must be promptly reported.

All SAEs that have not resolved by the end of the study, or that have not resolved upon discontinuation of the subject's participation in the study, must be followed until any of the following occurs:

- The event resolves.
- The event stabilizes.
- The event returns to baseline, if a baseline value/status is available.
- The event can be attributed to agents other than the IP or to factors unrelated to study conduct.
- It becomes unlikely that any additional information can be obtained (subject or health care practitioner refusal to provide additional information, lost to follow-up after demonstration of due diligence with follow-up efforts).

7.5. Pregnancies

All initial reports of pregnancy must be reported to the Sponsor within 24 hours of the Investigator knowledge of the event using the appropriate pregnancy form.

For IP, an exposure during pregnancy occurs if:

- A female becomes, or is found to be, pregnant either while receiving or having been directly exposed (e.g., environmental exposure) to the IP, or the female becomes, or is found to be, pregnant after discontinuing and/or being directly exposed to the IP (maternal exposure) for 28 days after last dose of or exposure to IP.

- A male partner of a pregnant female has been exposed to the IP, either due to treatment or environmental exposure, within 3 months prior to the time of conception and/or is exposed during his partner's pregnancy (paternal exposure).

If any study subject or study subject's partner becomes or is found to be pregnant during the study subject's treatment with the IP or exposure as defined above, the Investigator must submit this information on a Pregnancy form to the Sponsor (or its designated representative). In addition, the Investigator must submit information regarding environmental exposure to an IP in a pregnant woman (e.g., a subject reports that she is pregnant and has been exposed to a cytotoxic product by inhalation or spillage) using the Pregnancy form. This must be done irrespective of whether an AE has occurred and within 24 hours of awareness of the pregnancy. The information submitted should include the anticipated date of delivery (see following information related to induced termination of pregnancy).

Follow-up is conducted to obtain pregnancy outcome information on all exposure during pregnancy reports with an unknown outcome. The Investigator will follow the pregnancy until completion or until pregnancy termination (e.g., induced abortion) and then notify the Sponsor or its designated representative of the outcome as a follow-up to the initial Pregnancy form. In the case of a live birth, the structural integrity of the neonate can be assessed at the time of birth. In the event of a termination, the reason(s) for termination should be specified and, if clinically possible, the structural integrity of the terminated fetus should be assessed by gross visual inspection (unless pre-procedure test findings are conclusive for a congenital anomaly and the findings are reported).

If the outcome of the pregnancy meets the criteria for immediate classification as an SAE (e.g., ectopic pregnancy, spontaneous abortion, intrauterine fetal demise, neonatal death, or congenital anomaly [including that in a live born, a terminated fetus, an intrauterine fetal demise, or a neonatal death]), the Investigator should follow the procedures for reporting SAEs.

Additional information about pregnancy outcomes that are classified as SAEs follows:

- "Spontaneous abortion" includes miscarriage and abortion.
- All neonatal deaths that occur within 1 month of birth should be reported, without regard to causality, as SAEs. In addition, infant deaths after 1 month should be reported as SAEs when the Investigator assesses the neonatal death as related to exposure to IP.

Additional information regarding the exposure during pregnancy may be requested by the Investigator. Follow-up information regarding the outcome of the pregnancy and any postnatal sequelae in the infant will be required.

8. Statistical Methods and Determination of Sample Size

8.1. Statistical and Analytical Plans

A brief description is given of the planned analysis methodology. Detailed descriptions of the statistical analysis methods and data conventions will be provided as a separate document; i.e., the Statistical Analysis Plan (SAP). The SAP may also include additional exploratory analyses not explicitly mentioned in the following sections. A detailed SAP will be finalized prior to final data base lock. Any significant changes to the analyses described in this protocol will be addressed in the SAP and the Clinical Study Report.

8.2. Determination of Sample Size

Assumption of sample size calculation:

- Study design: Simon's optimal two stage design¹
- Type I error (one-sided): 5%
- Power: 80%
- Response probability of null hypothesis (P0): 0.05
- Response probability of SCB01A (P1): 0.20

According to these hypotheses, up to 37 subjects need to be recruited into the study (including 10 evaluable subjects in the Stage I and 19 evaluable subjects in Stage II, with the additional 8 subjects to account for replacement of subjects those who withdraw, i.e. dropout rate is 20%). At least 4 subjects are required to achieve CR or PR after treatment with SCB01A for the study to meet its primary objective. The trial will be discontinued if no objective response is observed after the Stage I tumor assessment review.

Stopping rule: The study will be stopped early for futility if less than 1/10 evaluable subjects showed ORR in Stage I; with no further investigation of the drug is less than 4/29 evaluable subjects achieve ORR by the end of Stage II.

8.3. Populations for Analysis

Subjects will be categorized into the following populations for analysis:

ITT population: The ITT population consists of all subjects enrolled in the study and received at least one study treatment.

Per-protocol (PP) population: The PP population will consist of all subjects who completed at least 3 cycles of study treatment regimen, have measurable baseline disease and at least one post-baseline RECIST assessment (PD, SD, PR or CR). Subjects with a major protocol violation, or AE, deemed by the Medical Monitor to have an impact on the study endpoints will be excluded from the PP population.

PK population: The PK population will consist of all subjects in stage I who received, at least, one dose of 24 mg/m² of SCB01A with sufficient post-dose bio-samples collected for PK profile characterization.

Details of any other populations for analysis will be described in the SAP.

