
 • Incidence and intensity of AEs evaluated using the CTCAE version 4.03 • Incidence and intensity of clinically significant abnormal laboratory values evaluated using the CTCAE version 4.03 • Percentage of subjects experiencing dose modifications including delays or omissions or discontinuation of study medication • Physical examination findings • Neurological examination findings • Vital signs measurements • ECG (including PR, QRS, QTc intervals) findings • Nerve conduction velocity examination (baseline for all subjects; symptom occurring and end of the study for subjects with grade 2 or greater neurological symptom) 
PK measurements:
 
PK will be performed on subjects enrolled in stage I.
 
 • PK blood samples will be taken immediately pre-infusion then at 24, 25, 26, 28, and 32 hours after the start of infusion on Days 1 and 8 of Cycle 3 if dose level of Cycle 3 is 24 mg/m² (time window at each sample collected: ±5 min). 	
Statistical Considerations:	
Populations for Analysis	
Study subjects will be categorized into the following populations for analysis:	

 • Intention-to-treat (ITT) population: The ITT population consists of all subjects enrolled in the study and received at least one study treatment. • Per-protocol (PP) population: The PP population will consist of all subjects who (1) withdraw from study for DLT, or (2) completed at least 3 cycles of study treatment regimen, have measurable baseline disease and, at least, one post-baseline RECIST assessment (PD, SD, PR or CR). Subjects with a major protocol deviation or AE, deemed by the Medical Monitor to have an impact on the study endpoints, will be excluded from the PP population. • PK population: The PK population will consist of all subjects in stage I who received, at least, one dose of 24 mg/m² of SCB01A with sufficient post-dose bio-samples collected for PK profile characterization. 
Details of any other populations for analysis will be described in the statistical analysis plan (SAP).
	
Statistical Analysis	
Assumption of sample size calculation:	

 • Study design: Simon's two stage design • Type I error (one-sided): 5% • Power: 80% 	

Name of Sponsor/Company: SynCore Biotechnology Co. Ltd.	
Name of Study Product: SCB01A	

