- b) Dose maintained: If clinical benefit observed at Dose 1 and without DLT, the dose level can be maintained until PD, intolerable toxicity, consent withdraw or death.
2. Dose 2 (18 mg/m²), will be administrated for one cycle and safety and clinical benefit observation will be performed prior to drug administration on Cycle 3 Day 1.
- a) Dose de-escalation: if any DLT experienced before Cycle 2 Day 8, the dose will be de-escalated to Dose 2a (15 mg/m²) for Cycle 2 Day 8. If first DLT during Cycle 2 is experienced after Cycle 2 Day 8, the dose will be de-escalated to Dose 2a (15 mg/m²) for Cycle 3. If no DLT is observed in Dose 2a, the subjects will receive the Dose 2a until PD, consent withdraw or death. Once more dose de-escalation (Dose 2b, 12 mg/m²) will be allowed if another DLT is observed in Dose 2a.
- b) Dose maintained: If clinical benefit observed at Dose 2 and without DLT, the Dose 2 can be continued until PD, intolerable toxicity, consent withdraw or death.
3. Dose 3 (24 mg/m²), will be administrated for one cycle and safety and tumor assessment will be performed prior to drug administration on Cycle 4 Day 1.
- a) Dose de-escalation: if any DLT experienced before Cycle 3 Day 8, the dose will be de-escalated to Dose 3a (20 mg/m²) for Cycle 3 Day 8. If first DLT during Cycle 3 is experienced after Cycle 3 Day 8, the dose will be de-escalated to Dose 3a (20 mg/m²) for Cycle 3. If no DLT is observed in Dose 3a, the subjects will receive the Dose 3a until PD, consent withdraw or death. Once more dose de-escalation (Dose 3b, 16 mg/m²) will be allowed if another DLT is observed in Dose 3a.

Figure 2: Dose Modification

If the subject experienced any neurotoxic DLT, the subject will be withdrawn.

Subjects will be considered to be non-evaluable for ORR if they receive study drug for fewer than 9 weeks (3 cycles) of treatment for any reason other than study-drug related toxicity. Non-evaluable subjects will be replaced.

All subjects will be treated until the occurrence of progressive disease, intolerable adverse events (AEs)/toxicity, consent withdrawal or death. After discontinuation of study treatment, all subjects will be followed for survival and disease-specific therapies of the clinician's choice will be administered. Follow-up visits will be scheduled every 3 weeks for 9 weeks (i.e. week 3, week 6, and week 9), thereafter every 9 weeks until the end of the study.

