## **9.7 STATISTICAL METHODS PLANNED IN THE PROTOCOL AND DETERMINATION OF SAMPLE SIZE**

### **9.7.1 Statistical and Analytical Plans**

#### **9.7.1.1 Populations for Analysis**

Study subjects were categorized into the following populations for analysis:

- Intention-to-treat (ITT) population: The ITT population consisted of all subjects enrolled in the study and received at least one study treatment.

- Per-protocol (PP) population: The PP population consisted of all subjects who (1) withdrew from study for DLT, or (2) completed at least 3 cycles of study treatment regimen, have measurable baseline disease and, at least, one post-baseline RECIST assessment (PD, SD, PR or CR). Subjects with a major protocol deviation or AE, deemed by the Medical Monitor to have an impact on the study endpoints, would be excluded from the PP population.
- PK population: The PK population consisted of all subjects in stage I who received, at least, one dose of 24 mg/m^2 of SCB01A with sufficient post-dose bio-samples collected for PK profile characterization.

Details of any other populations for analysis were described in the statistical analysis plan (SAP).

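### The evaluable/per-protocol set that decides efficacy is not defined consistently for subjects who stop before 3 cycles because of toxicity

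*Protocol*

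**What the plan says.** The synopsis (Statistical Analysis) and SAP 9.7.1.2 base the efficacy conclusion on the PP population. The synopsis (Trial Design) equates PP subjects with those evaluable for the objective response rate (ORR) and says that non-evaluable subjects are replaced. Protocol 8.2 applies the 1/10 and 4/29 rules to evaluable subjects.

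For a subject who stops before 3 cycles because of toxicity, the texts differ:

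- **Protocol 8.3:** "The PP population will consist of all subjects who completed at least 3 cycles of study treatment regimen". Measurable baseline disease and a post-baseline assessment are also required. There is no toxicity or DLT exception.
- **Protocol synopsis, Populations for Analysis:** "The PP population will consist of all subjects who (1) withdraw from study for DLT, or (2) completed at least 3 cycles".
- **SAP 9.7.1.1:** "all subjects who (1) withdrew from study for DLT, or (2) completed at least 3 cycles of study treatment regimen", which matches the synopsis.
- **Protocol 3.1:** a subject with fewer than 3 cycles is non-evaluable "for any reason other than study-drug related toxicity. Non-evaluable subjects will be replaced". A stop for any drug-related toxicity, DLT or not, therefore stays evaluable and is not replaced.

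Three other provisions bear on the point. The synopsis ORR definition and SAP 9.8 count DLT withdrawals as non-responders. All the PP definitions let the Medical Monitor exclude a subject for an adverse event judged to affect the endpoints. Protocol 6.1 gives a further wording of evaluable (a baseline and at least one on-study assessment) and still carries a drafting note that it should be revised if a synopsis revision is accepted.

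**The concern.** A subject who withdraws for a DLT in Cycle 2 is outside PP under Protocol 8.3, but is inside it as a non-responder under the synopsis and SAP. A subject who stops in Cycle 2 for drug toxicity that is not a DLT is evaluable and not replaced under Protocol 3.1, but is outside PP under the other three texts. The protocol thus contradicts itself, and the SAP does not remove every conflict.

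The design has 29 evaluable subjects and needs 4 responders, so membership matters. Dropping subjects who failed through toxicity and enrolling others in their place selects the evaluable set on outcome. It raises the ORR on which the decision is made and lifts the type I error above the planned level. An open choice of definition also leaves room to settle the denominator after responses are known.

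**Working it through.** **1. Reproduce the design.** Inputs from Protocol 8.2: "Study design: Simon's optimal two stage design", "Type I error (one-sided): 5"%, power 80%, "Response probability of null hypothesis (P0): 0.05", "Response probability of SCB01A (P1): 0.20". Stage I has 10 subjects and stops at 0 responses. The total is 29, with success at 4 or more.

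P(success | p) = Σ (x = 1 to 3) P(X₁ = x) · P(X₂ ≥ 4 − x) + P(X₁ ≥ 4), with X₁ ~ Bin(10, p) and X₂ ~ Bin(19, p).

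- p = 0.05: 0.3151 × 0.0665 + 0.0746 × 0.2453 + 0.0105 × 0.6226 + 0.0010 = 0.0468.
- p = 0.20: 0.2684 × 0.7631 + 0.3020 × 0.9171 + 0.2013 × 0.9856 + 0.1209 = 0.8011.

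A search over two-stage designs confirms 0/10, 3/29 as the optimal design for these inputs. With 20% dropout, 29/0.8 = 36.25, which rounds up to 37. The sample size is not in error.

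**2. Effect of dropping and replacing toxicity stops.** Let d be the share of treated subjects who stop before 3 cycles for toxicity, all of them non-responders. If they are kept, the ORR is p. If they are dropped and replaced, the ORR in the evaluable set is p/(1 − d). At a true ORR of 5% with these subjects counted:

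| d (assumed) | 0.05/(1 − d) | Type I error |
|---|---|---|
| 0 | 0.0500 | 4.7% |
| 5% | 0.0526 | 5.5% |
| 6% | 0.0532 | 5.6% |
| 10% | 0.0556 | 6.4% |
| 20% | 0.0625 | 9.0% |

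**3. Effect on the denominator (invented counts, before any replacement).** Take 29 treated subjects, of whom 4 withdraw for DLT and 2 for other drug-related toxicity before 3 cycles, with the rest meeting all PP criteria. Four responders then give:

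- Protocol 3.1: 4/29 = 13.8%
- Synopsis and SAP: 4/27 = 14.8%
- Protocol 8.3: 4/23 = 17.4%

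**4. What the documents say about d.** They do not give it. Protocol 1.2 reports 5 DLTs in the phase I study of 33 subjects, but also that 31 of the 33 completed the main treatment, so at most 2/33 = 6% did not. Protocol 3.1 generally answers a DLT with dose reduction and states withdrawal for neurotoxic DLTs. DLT occurrence is therefore not the withdrawal fraction. Phase I also used a different schedule, so neither rate carries over firmly. SAP 9.8 mentions 5 subjects not evaluated because of clinical progression or AE/SAE, without a split.

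**The case against.** The strongest reply is that this is an unsynchronised edit, not a set of rival analysis sets. PP itself has only two wordings, because Protocol 3.1 speaks of evaluability and replacement and never names PP. Protocol 8.1 sends detailed methods to the SAP, the SAP agrees with the synopsis, and counting DLT withdrawals as non-responders makes sense only if they are in the set. The note left in Protocol 6.1 suggests body text that lagged behind the synopsis. The DLT list is also broad, so few toxicity stops would fall outside it.

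Much of this stands. The SAP wording can settle Protocol 8.3 for the final analysis, and the inflation in step 2 belongs chiefly to the 8.3 reading. Three things remain. The synopsis ties PP to evaluability, so the Protocol 3.1 rule does bear on PP. Replacement and the Stage I 1/10 count are run during the trial, before a final analysis can settle anything. SAP 9.8 lists exceptions and clarifications to the protocol without naming the PP definition; its ORR entry deals with responder status, not set membership.

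Two stronger readings are tempting but not supported:

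- **Loss of power.** A reader might infer that enrolment stops at 29 evaluable under Protocol 3.1 while PP holds, say, 26 or 24, so that power falls to 75.0% or 70.4%. That holds p = 0.20 on the smaller set, although the subjects removed are all non-responders. The rule counts responders, and removing non-responders does not change the count. With p rescaled as in step 2 (0.20 × 29/26 = 0.223; 0.20 × 29/24 = 0.242, losses in Stage II), power is 82.4% and 83.8%.
- **A 15% withdrawal rate.** A reader might take 5 DLTs in 33 as an estimate of d. Step 4 shows why it is not one.

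**Conclusion.** The inconsistency is in the text and does not depend on any assumed rate. It should be fixed, but it does not undermine the design, whose stated error rates reproduce. If toxicity non-responders are dropped and replaced, the type I error is about 5.5% to 9.0% for an assumed d of 5% to 20%, against 4.7% as designed. That range assumes that every such subject is a non-responder and is replaced by a subject from the remaining population. The actual effect in this trial cannot be computed from the documents, and it is nil if nobody stopped before 3 cycles for toxicity. No loss of power is shown.

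**What to change.** Use one definition in the synopsis (Trial Design and Populations for Analysis), Protocol 3.1, 6.1 and 8.3, and SAP 9.7.1.1: every treated subject who stops before 3 cycles for study-drug related toxicity, DLT or not, belongs to the PP/evaluable set, is not replaced and counts as a non-responder. This agrees with how the synopsis ORR definition and SAP 9.8 count DLT withdrawals. It should carry no exception for a response confirmed earlier, because that would conflict with the synopsis, and the first scheduled scan comes only after Cycle 3. State also that the Medical Monitor's adverse-event exclusion cannot remove these subjects, remove the drafting note from Protocol 6.1, and list the PP clarification in SAP 9.8.

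The cost is wording in five protocol places and the SAP. The reported ORR may be slightly lower.

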8.4. Safety Analysis

Safety profile will be evaluated by the following endpoints.

- Incidence and intensity of AEs evaluated using the CTCAE version 4.03
- Incidence and intensity of clinically significant abnormal laboratory values evaluated using the CTCAE version 4.03
 - Percentage of subjects experiencing dose adjustments, including delays or omissions or discontinuation of study medication
- Physical examination findings
- Vital signs measurements
- ECG (including PR, QRS, QTc intervals) findings
- Nerve conduction velocity examination (baseline for all subjects; symptom occurring and end of study for subjects with grade 2 or greater neurological symptom)

All safety endpoint data will be listed and summarized for each dose and day within cycle using descriptive statistics. The change from baseline data for the safety endpoints will also be summarized using descriptive statistics.

Number and percentage of subjects experiencing at least one DLT or AE will be tabulated by dose. Further details regarding any DLTs or AEs experienced will be provided in data listings. All recorded AEs will be listed and tabulated by system organ class and preferred term using the Medical Dictionary for Regulatory Activities (MedDRA) and by dose level. The incidence of Treatment Emergent AEs (TEAEs) during the study period will be tabulated by dose group, body system, and preferred term. TEAEs are those events that occur or worsen on or after first dose of IP and up to 28 days after the last dose. TEAEs are AEs with onset dates on or after the first dosing date. Those with missing onset dates will be included as treatment emergent. Number and percentage of subjects who withdrew/stopped dosing will be tabulated. Number and percentage of subjects who missed 1 or more doses (1 dose, 2 doses, etc.) in any cycle will be tabulated by cycle.

Serious AEs, Grade 3 and above AEs, AEs related to study treatment, and AEs causing discontinuation will be tabulated. AEs for individual subjects will be listed, along with information regarding onset, duration, severity, and relationship to study treatment.

Vital signs, physical examination, ECG, and clinical laboratory test results will be listed and summarized by dose group, cycle and day within cycle as applicable and may be presented graphically. Any significant or outside normal range limits value for vital signs, physical examination, ECG, or clinical laboratory results will be listed.

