6.2. Dose Limiting Toxicity (DLT)

All toxicities will be classified according to the NCI Common Terminology Criteria for AEs (CTCAE) version 4.03.

DLT will be defined as the occurrence of any of the following criteria unless there is definitive alternative evidence that administration of SCB01A did not cause the specific toxicity:

- Grade 4 neutropenia exceeding 5 days' duration
- Grade 4 thrombocytopenia
- Grade 4 anemia
- Grade 3 or greater neutropenia with complications (e.g., fever, infection etc.)

- Grade 3 or greater thrombocytopenia with complications (e.g., bleeding)
- Grade 3 or greater non-hematological AEs including Grade 3 unmanageable nausea and vomiting that persist for 3 or more days after drug administration. Grade 3 fatigue lasting for ≤ 1 week is not considered as a DLT
- Grade 3 or greater prolonged QTc interval
- Grade 3 or greater neurotoxicity
- Delayed treatment exceeding 14 days duration due to drug-related toxicity.
- Not able to recover from grade 2 neurotoxicity exceeding 3 weeks

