7.1. Adverse Events

An AE is any untoward medical occurrence that occurs in a patient or clinical investigation subject administered a pharmaceutical product, and which does not necessarily have to have a causal relationship with this treatment. An AE can therefore be any unfavorable and unintended sign (including abnormal laboratory finding), symptom, or disease temporally associated with the use of an IP, whether or not considered related to the medicinal product (definition per ICH E2A and E6 R1).

All AEs, regardless of seriousness, severity, or presumed relationship to study therapy, must be recorded using medical terminology on the AE CRF page. Whenever possible, diagnoses should be given when signs and symptoms are due to a common etiology (e.g., cough, runny nose, sneezing, sore throat, and head congestion should be reported as “upper respiratory infection”). All measures required for AE management must be recorded in the source document and reported according to Sponsor instructions.

For all AEs, the Investigator must pursue and obtain information adequate to both determine the outcome of the AE and to assess whether it meets the criteria for classification as an SAE (see Section on SAEs) requiring immediate notification to the Sponsor or its designated representative. For all AEs, sufficient information should be obtained by the Investigator to determine the causality of the AE.

Interventions for pre-treatment conditions (e.g., elective cosmetic surgery) or medical procedures that were planned before study enrolment are not considered AE.

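### The graded laboratory endpoint counts only values labelled clinically significant, an undefined term, so its table may understate Grade 3-4 laboratory toxicity

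*Protocol*

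**What the plan says.** The Protocol states the graded laboratory endpoint in the same words in three places: the synopsis (safety measurements), section 6.3 and section 8.4. It is "Incidence and intensity of clinically significant abnormal laboratory values evaluated using the CTCAE version 4.03". None of them gives a definition, a grade threshold or an assessor for the qualifying term. Section 5.7, which covers the laboratory assessments, does not supply one either.

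Section 8.4 plans two further laboratory outputs that do not use the label as a condition:

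- Summaries: "clinical laboratory test results will be listed and summarized by dose group, cycle and day within cycle as applicable".
- Listings: "Any significant or outside normal range limits value for vital signs, physical examination, ECG, or clinical laboratory results will be listed".

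Laboratory abnormalities can also reach the tables by two other routes:

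- **Adverse events.** Section 7.1 says "An AE can therefore be any unfavorable and unintended sign (including abnormal laboratory finding", and that "All AEs, regardless of seriousness, severity, or presumed relationship to study therapy, must be recorded using medical terminology on the AE CRF page". Section 8.4 adds that "Serious AEs, Grade 3 and above AEs, AEs related to study treatment, and AEs causing discontinuation will be tabulated".
- **Dose-limiting toxicities (DLTs).** Section 6.2 defines these by grade, for example "Grade 4 thrombocytopenia" and "Grade 3 or greater non-hematological AEs including Grade 3 unmanageable nausea and vomiting". Section 8.4 tabulates the number and percentage of subjects with at least one.

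The SAP text supplied contains no laboratory analysis.

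**The concern.** CTCAE grades can be assigned from the measured values, and those values are collected anyway. Section 5.7 and Table 1 schedule haematology, chemistry and coagulation at screening, at every clinic visit (including Day 15 of Cycles 1 to 3) and at end of treatment. Requiring a value to be called clinically significant before it counts adds a judgement that the grading does not need, and the documents leave that judgement undefined.

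Safety and toxicity is a secondary objective (section 2.2), and several DLT criteria are blood-count grades. A reader of the report will look to this table for the proportion of subjects who reached Grade 3 or 4 on each test. If entry depends on an undefined label, that proportion reflects labelling practice as well as the drug. With up to 4 centres and no common rule, the practice could differ between them.

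**Working it through.** **The plan's own figures.** The documents state no laboratory toxicity rate, so there is none to reproduce. The sample size does not bear on this point and is unaffected. For the record, the design of 10 + 19 = 29 evaluable subjects, continuing with at least 1/10 and succeeding with at least 4/29, has exact one-sided alpha 0.0468 and power 0.8011. The enrolment cap follows from 29 / (1 - 0.20) = 36.25, rounded up to 37.

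**Step 1: which output gives a proportion of subjects by grade?**

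| Planned output | Uses the label? | Gives % of subjects by laboratory grade? |
|---|---|---|
| Graded laboratory endpoint (8.4, 6.3, synopsis) | Yes | Yes, labelled values only |
| Summaries by dose, cycle and day (8.4) | No | No |
| Listing of significant or out-of-range values (8.4) | No; out of range is enough | No |
| AE tables, including Grade 3 and above (8.4) | No | Only for findings recorded as AEs |
| DLT table (8.4, criteria in 6.2) | No | Only for findings that meet a DLT criterion |

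The summaries cannot stand in for the graded table. Each subject's dose can change from cycle to cycle (section 3.1), so a summary by dose and day does not collect a subject's worst value.

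**Step 2: what can miss every graded table?** Compare the blood-count criteria in section 6.2 with the possible results:

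- Grade 4 platelets and Grade 4 anaemia are DLTs on grade alone.
- Grade 4 neutropenia counts if it exceeds 5 days, or earlier if complicated.
- Grade 3 neutropenia and Grade 3 thrombocytopenia count only with complications.
- Grade 3 anaemia is not among the haematological criteria.
- Liver tests can enter only through the non-haematological criterion, which is worded in terms of AEs and so needs the finding to be recorded as one.
- A separate criterion catches any drug-related toxicity that delays treatment by more than 14 days.

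This leaves uncomplicated Grade 3 cytopenias, and uncomplicated Grade 4 neutropenia of 5 days or less, that cause no such delay. If not labelled and not recorded as AEs, they appear in no table that counts subjects by grade.

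**Step 3: direction.** Labelled Grade 3-4 values are a subset of all Grade 3-4 values. The labelled incidence is therefore equal to or lower than the incidence from the measured results, and never higher.

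**Step 4: illustration of size (assumed inputs).** Let p be the true proportion of subjects with a Grade 3-4 result on a test, and s the share of those subjects with at least one such result labelled. Then:

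- shown rate = p × s
- subjects shown = 37 × p × s

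With p = 20%, the true count is 37 × 0.20 = 7.4 subjects.

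| s | Shown rate | Subjects shown |
|---|---|---|
| 100% | 20% | 7.4 |
| 80% | 16% | 5.9 |
| 50% | 10% | 3.7 |
| 25% | 5% | 1.9 |

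For p from 10% to 40% and s from 25% to 100%, the shown rate runs from 0.10 × 0.25 = 2.5% to 0.40 × 1.00 = 40%. At s = 100% nothing is lost. The documents give neither p nor s.

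**The case against.** The strongest reply is that the safety plan does not rest on this one endpoint. The AE definition includes abnormal laboratory findings with no significance condition, all AEs must be recorded, and Grade 3 and above AEs are tabulated. The DLT criteria work by grade. The synopsis also lists changes in laboratory data as a safety endpoint without any filter. A reader might infer that unlabelled Grade 3-4 results vanish from the safety reporting. The documents do not support that: the values remain in the summaries and listings, and many have a route into the AE or DLT tables.

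What this does not answer is the count by grade. Section 7.1 says an AE can be an abnormal laboratory finding. It does not say that every Grade 3-4 value must be recorded as one, so that route also depends on a recording judgement. Step 2 shows that the DLT table does not cover the remainder.

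A reader might also infer that the open-label investigator applies the label. The Protocol gives the investigator that role for ECGs (section 5.6) and physical examination (section 5.2), but names nobody for laboratory values. The missing assessor is part of the gap; it is not evidence about who decides.

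A further fair point is that section 8.1 leaves detailed methods to a separate SAP. The SAP text supplied begins mid-sentence, has no safety analysis section and itself refers to a separate plan. Worst-grade or shift tables may therefore be specified elsewhere. That limits any claim about what was finally produced. It does not change the Protocol's endpoint, which carries the restriction in all three places.

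**Conclusion.** The point holds as a limited one. The only laboratory incidence endpoint by CTCAE grade in these documents is restricted by a term with no definition and no named assessor for laboratory results. Its table may therefore understate Grade 3-4 laboratory toxicity, chiefly uncomplicated Grade 3 cytopenias and short uncomplicated Grade 4 neutropenia.

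It would go too far to say that haematological or liver toxicity is understated. Nothing in the documents shows that any Grade 3-4 value would go unlabelled. The size cannot be computed, and the figures in the illustration rest on assumed toxicity and labelling rates. Only the direction is certain: relative to grading all measured values, the restriction can lower the count or leave it unchanged.

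Severity is low. Safety is a secondary objective in a single-arm trial, the stage decisions rest on response, and no sample size, error rate or decision rule depends on this table. It is worth changing because the change is cheap and removes an avoidable one-directional error.

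**What to change.** In Protocol sections 8.4 and 6.3 and in the synopsis:

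1. Remove the clinical-significance condition from the graded laboratory endpoint.
2. Derive the CTCAE version 4.03 grade by program from every recorded result of each gradable haematology, chemistry and coagulation test.
3. Tabulate the worst post-baseline grade per subject for each test, and the shift from baseline grade to worst grade.
4. Keep any clinical-significance flag as a column in the listings.

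Cost: revised wording and a little more standard programming on data already collected. Tests graded against a normal limit need each local laboratory's reference range, which the out-of-range listing in section 8.4 already requires. The downside is that reported laboratory toxicity rates may be somewhat higher.
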